This proposal is a phase II study that will evaluate the safety and efficacy of silymarin for the treatment of subjects with chronic hepatitis C who did not respond to conventional antiviral therapy. The primary objectives of this study are to assess the safety and adverse event profile of silymarin over a range of doses compared to placebo and to assess efficacy of silymarin in normalizing serum aminotransferase activity in patients with chronic hepatitis C. Secondary objectives are to characterize the effect of silymarin on serum levels of HCV RNA and to explore relationships between silymarin therapy and serum biomarkers of HCV hepatic disease activity (oxidative stress, apoptosis, and fibrogenesis).

Eligible subjects will be randomized to treatment with placebo or one of two dosages selected from the phase I study: Legalon[®] 420 mg or 700 mg administered orally thrice daily.

Investigators and subjects will be masked to treatment assignment. The study design includes a screening period during which patients will undergo full medical evaluation to verify protocol eligibility and a treatment period of 24 weeks during which time clinic visits and laboratory studies will be performed every 2-4 weeks to monitor for safety and efficacy of therapy. Subjects will continue to be followed for an additional 12 weeks after the completion of study medication to monitor for adverse events and investigate post-treatment outcomes. Blood will be collected for pharmacokinetic analysis for confirming estimates of PK parameters obtained during phase I, for measuring biomarkers, and for storage for future studies.

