3.4.4 Safety measurements

Laboratory evaluations: Participants will undergo laboratory tests according to the time and event schedule to monitor for medication toxicities.

Adverse event monitoring: Participants will be queried by study personnel at each study visit about the incidence of adverse events. These will be documented in the study record and classified according to duration, severity, relationship to study medication, and action with study medication. Serious adverse events will be reported to appropriate regulatory authorities, in addition to the DSMB as below, in a timely fashion.

In the event that an investigator considers an adverse event to be related to study medication, the investigator may submit an unmask request to the clinical center investigational pharmacist to unmask the study drug dose, per the study specific unmasking procedure.

Pregnancy: Women of child-bearing potential will have a urine pregnancy test performed within 24 hours of the first administration of study drugs, monthly for the duration of therapy, and at 1 month following completion of therapy.

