Baseline	(Day	(0)) visit

Silymarin level	
HCV RNA	Serum 3ml (stored)
Sample storage	Fasting 10ml serum and 5ml plasma
Pregnancy Test	Urine, pre-dose
Adherence counseling	Use of MATI guidelines
Medication Education	Use of Medi-dose cups and patient diaries that record doses taken and alcohol use
Study Medication Administration	Supervised by research coordinator
Questionnaires	SF-36, CLDQ, CES-D, ASE

4.3 Treatment Period: Silymarin and/or placebo will be administered as a total of 5 capsules administered three times daily. Treatment will be continued for 24 weeks. During the treatment period, participants will return for safety and efficacy evaluations at treatment weeks 2, 4, 8, 12, 20, 24 (end of treatment). Phone calls will be made to the participants at weeks 6 and 16 to monitor safety, compliance with study medication and concurrent medications. There is an acceptable window of +/- 3 days for all visits. The following procedures will be performed at the study visits:

Vital signs and weight at each visit; physical exam every 3 months or
as needed
Each visit
Each visit
Each visit
Each visit; ALT, AST, AlkPO4, total bilirubin, albumin, BUN, creatinine,
glucose.
Week 12 and 24 only: fasting triglycerides, glucose, insulin
Urine, each visit
Week 24
Week 24
Weeks 2, 4, 12, 24
Weeks 12, 24 (3 ml serum, stored)
Week 12
Fasting 5ml serum and 3ml plasma at weeks 12 and 24 only
Each visit according to assigned schedule or random sample
each visit
Weeks 4, 12, 24: SF-36, CLDQ, CES-D, ASE
Each visit

Table 5Safety and Efficacy Visits

Monitoring and	Monitoring by dose counts and review of diary entries
Counseling	

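### The protocol requires a monthly on-treatment pregnancy test, but the visit schedule has an 8-week gap (weeks 12 to 20) with no visit for the week-16 test

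*Protocol*

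**What the plan says.** Four places in the protocol bear on this.

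- **Section 3.4.4 (Safety measurements, pregnancy).** Women of child-bearing potential are tested within 24 hours of the first administration, then "monthly for the duration of therapy, and at 1 month following completion of therapy".
- **Section 4.3 (Treatment Period), visits.** The visit list is given in running text: "participants will return for safety and efficacy evaluations at treatment weeks 2, 4, 8, 12, 20, 24 (end of treatment". The window is also stated there: "There is an acceptable window of +/- 3 days for all visits". Section 4.3.1 repeats the same visit weeks for the random pharmacokinetic samples.
- **Section 4.3, telephone contacts and Table 5.** "Phone calls will be made to the participants at weeks 6 and 16 to monitor safety, compliance with study medication and concurrent medications". No specimen or home test is attached to either call. Table 5 gives chemistry at each visit, and its pregnancy-test entry reads "Urine, each visit".
- **Protocol summary.** The study is described as having "a treatment period of 24 weeks during which time clinic visits and laboratory studies will be performed every 2-4 weeks".

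For follow-up, Table 6 in section 4.4 places a urine pregnancy test at post-treatment week 4.

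**The concern.** A site that follows section 4.3 will not do the pregnancy test that section 3.4.4 requires around week 16. A site that follows section 3.4.4 has no scheduled visit at which to do it. Every woman of child-bearing potential who is on treatment through that period therefore either misses a stated safeguard or needs a contact that the schedule does not provide. The protocol plainly treats pregnancy as a safety matter: section 3.3 requires a negative test before the first dose and two forms of contraception, and excludes women who are pregnant, breast-feeding or contemplating pregnancy.

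The laboratory schedule raises a smaller version of the same problem. The summary tells a reader, an ethics board or a monitoring board that laboratory studies are never more than four weeks apart on treatment. The schedule in section 4.3 leaves eight weeks between two of them.

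Neither matter affects the definition of the week-24 primary endpoint, the randomization or the power calculation. This is a consistency problem in safety monitoring.

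**Working it through.** **Inputs.** Visit weeks 0 (baseline), 2, 4, 8, 12, 20 and 24, from sections 4.2 and 4.3. Visit window of 3 days either side, from section 4.3. Stated intervals: monthly for the pregnancy test (section 3.4.4) and 2 to 4 weeks for clinic visits and laboratory studies (summary).

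**Formula.** Nominal gap in days = 7 × (later week − earlier week). The shortest permitted gap subtracts 3 days for each visit that has a window, and the longest adds them. Baseline is taken as day 0 without a window.

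| From week | To week | Gap (weeks) | Gap (days) | Range with windows (days) | Nominal gap within 2 to 4 weeks? |
|---|---|---|---|---|---|
| 0 | 2 | 2 | 14 | 11 to 17 | yes |
| 2 | 4 | 2 | 14 | 8 to 20 | yes |
| 4 | 8 | 4 | 28 | 22 to 34 | yes |
| 8 | 12 | 4 | 28 | 22 to 34 | yes |
| 12 | 20 | 8 | 56 | 50 to 62 | **no** |
| 20 | 24 | 4 | 28 | 22 to 34 | yes |

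**Reproducing the stated interval.** Five of the six gaps fit the summary's 2 to 4 weeks. The sixth is 8 / 4 = 2 times the stated maximum.

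**Can the windows close the gap?** No. The shortest permitted gap is 56 − 3 − 3 = 50 days, which exceeds both 28 days and the longest calendar month (31 days). Week 16 is day 16 × 7 = 112. The latest permitted week-12 visit is day 84 + 3 = 87, and the earliest permitted week-20 visit is day 140 − 3 = 137. Each is 25 days from day 112, so neither can serve as the week-16 test.

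**Which monthly tests are affected?** The 4-weekly points on treatment are weeks 4, 8, 12, 16, 20 and 24. Five of the six coincide with a visit. Only week 16 does not.

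**Post-treatment test.** Table 6 places it at post-treatment week 4, which agrees with section 3.4.4. The later 8-week interval between the two follow-up visits (post-treatment weeks 4 and 12) contradicts nothing, because the monthly rule and the 2 to 4 week statement both concern the treatment period.

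**Does any other text supply the missing contact?** The week-16 telephone call covers safety, compliance and concurrent medications, with no test described. Unscheduled visits under section 4.5 are triggered by symptoms or by a need to repeat laboratory tests, so they do not provide routine testing.

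**The case against.** The strongest reply is that this is one missed contact in an otherwise consistent schedule, with mitigation in place. Much of that stands. The week-16 call is a safety contact, two forms of contraception are required, and unscheduled visits are available. These limit the likely harm, but none of them is a pregnancy test, so they do not remove the contradiction.

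A second reply is that the laboratory half is weaker than the pregnancy half. This is correct. Section 3.4.4 sets no laboratory interval of its own and defers to the time and event schedule. On laboratory tests, the only text that conflicts with section 4.3 is the sentence in the summary.

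A third reply is that some of the evidence cannot be seen. Appendix 5 (the time event table) is listed but not included in the text at hand, and Table 5 is read here without legible row labels. Taking its urine entry as the pregnancy test is an inference. Tables 3, 4 and 6 support it, since each gives urine as the pregnancy-test specimen. The main point does not depend on it, because section 4.3 has no week-16 visit whatever the row means. If Appendix 5 did show a week-16 test, it would disagree with sections 4.3 and 4.3.1, and reconciliation would still be needed.

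A reader might infer more than the document supports in three ways:

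- **That the monthly test and the 2 to 4 week interval fail throughout the trial.** They do not. The conflict is confined to weeks 12 to 20.
- **That the grade 2 dose-reduction rule in section 3.4.2, which looks across two consecutive safety visits, is broken by the gap.** That rule states no maximum interval, is discretionary and is described as guidance, and section 4.5 allows extra visits. Nothing is contradicted there.
- **That participants are misinformed in the consent form.** The form is not available here, so nothing can be said about it.

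**Conclusion.** The point holds for weeks 12 to 20. The monthly on-treatment pregnancy test in section 3.4.4 cannot be delivered by the visits in section 4.3: one of the six 4-weekly tests, at week 16, has no scheduled visit, and the surrounding gap is 56 days (50 to 62 with windows). Measured against a 4-week interval, the excess is 4 weeks and one test. It concerns each woman of child-bearing potential on treatment through that window; the protocol does not say how many that will be.

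The secondary point also holds. The same gap contradicts the summary's 2 to 4 week statement for clinic visits and laboratory studies, and it applies to all participants. It carries less weight because it rests on a descriptive sentence in the summary.

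The conclusion assumes that monthly means roughly every 4 weeks or each calendar month (both readings give the same answer), that the 4-week gaps are judged at their nominal dates (the windows allow up to 34 days), and that the visit list in sections 4.3 and 4.3.1 is the operative one. It should be corrected, but it does not touch the efficacy analysis.

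**What to change.** Reconcile the protocol summary, section 3.4.4 and section 4.3 with its Table 5, so that the stated pregnancy-test interval and the stated laboratory interval both match the scheduled contacts. Check Appendix 5 at the same time, so that the time event table and the body text give one schedule. State the pregnancy-test and laboratory intervals separately if they are meant to differ. Whether the stated intervals or the scheduled contacts should change is for the clinical team to decide.

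The cost is small: a wording correction or, depending on that choice, one added pregnancy test for women of child-bearing potential, or one added laboratory sample per participant. Sample size and analysis are unaffected.

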3.5 Premature discontinuation

Treatment may be discontinued prematurely for the following reasons:

- 1. Participant requests termination of the study medication;
- 2. Participant is intolerant of the study medication despite predetermined dose reductions and side effect management strategies;
- 3. Safety concerns at the discretion of the investigator. These concerns will be documented in the source documents.

Participants who discontinue treatment prematurely for the above reasons will be encouraged to remain in the post-treatment follow-up period for an additional 12 weeks, unless they withdraw consent. For those discontinued prematurely, data and blood samples will be obtained as listed for the week 24 end-of-treatment visit.

4.0 Study visits (Appendix 5)

4.1 Screening Visit: The first screening visit will take place no more than 30 days prior to anticipated dose initiation. Written informed consent will be obtained prior to any screening evaluations. This initial screening visit will be used to determine patient eligibility as per the inclusion and exclusion criteria.

	Screening visit 1
Informed Consent	Main study
Medical History and	
Complete Physical	
CBC/Differential	
Chemistry	ALT, AST, AlkPO4, total bilirubin, albumin, BUN, creatinine, sodium,
Coagulation Tests	PT or INR
Thyroid Test	TSH
Pregnancy Test	Urine
Viral Serology	Drawn at screening (historical acceptable if after end of previous
	therapy): HCV RNA quantitative
	Documented within 5 years: HBsAg, anti-HIV
	HCV genotype (historical acceptable)
Other Serology and	Fe, TIBC, ferritin, iron saturation
Chemistry	Anti-nuclear antibody (historical acceptable)
EKG	

Table 3 Screening Visit 1

4.1.1 Re-screen Criteria and Procedures: If the period between the initiation of screening and the Baseline visit is more than 30 days, but less than or equal to 6 weeks (42 days), a complete re-screen is not required. However, if the period exceeds 6 weeks (42 days), the screening evaluation must be repeated in its entirety.

Partial Re-screen (31-42 days elapsed between the initiation of screening and Baseline)

- The following laboratory tests must be repeated:
 - Liver function tests
 - o CBC
 - o Chem-7
 - Pregnancy test (where applicable)

Complete Re-screen (> 42 days elapsed between the initiation of screening and Baseline)

- Repeat the entire screening evaluation
- Repeat all labs required for screening evaluation
- Obtain blood samples for HCV-RNA test

4.2 Baseline visit (Day 0): Once the patient has been confirmed to be eligible and has completed the first screening visit, he/she will return for additional laboratory studies and comprehensive instruction in study procedures and medication administration by study personnel. These two visits, screening and baseline (day 0) will occur within 30 days. If the patient provides informed consent for the genetic component of the study, a 20ml sample of whole blood will be collected at the Baseline visit or at any of the subsequent protocol visits throughout the course of the study.

	Baseline (Day 0) visit
Interim Medical	
History	
CBC/Differential	
Chemistry	ALT, AST, AlkPO4, total bilirubin, fasting triglycerides and cholesterol, glucose, and insulin

Та	ble 4	4	
Baseline	(Day	(0)) visit

Silymarin level	
HCV RNA	Serum 3ml (stored)
Sample storage	Fasting 10ml serum and 5ml plasma
Pregnancy Test	Urine, pre-dose
Adherence counseling	Use of MATI guidelines
Medication Education	Use of Medi-dose cups and patient diaries that record doses taken and alcohol use
Study Medication Administration	Supervised by research coordinator
Questionnaires	SF-36, CLDQ, CES-D, ASE

4.3 Treatment Period: Silymarin and/or placebo will be administered as a total of 5 capsules administered three times daily. Treatment will be continued for 24 weeks. During the treatment period, participants will return for safety and efficacy evaluations at treatment weeks 2, 4, 8, 12, 20, 24 (end of treatment). Phone calls will be made to the participants at weeks 6 and 16 to monitor safety, compliance with study medication and concurrent medications. There is an acceptable window of +/- 3 days for all visits. The following procedures will be performed at the study visits:

Vital signs and weight at each visit; physical exam every 3 months or
as needed
Each visit
Each visit
Each visit
Each visit; ALT, AST, AlkPO4, total bilirubin, albumin, BUN, creatinine,
glucose.
Week 12 and 24 only: fasting triglycerides, glucose, insulin
Urine, each visit
Week 24
Week 24
Weeks 2, 4, 12, 24
Weeks 12, 24 (3 ml serum, stored)
Week 12
Fasting 5ml serum and 3ml plasma at weeks 12 and 24 only
Each visit according to assigned schedule or random sample
each visit
Weeks 4, 12, 24: SF-36, CLDQ, CES-D, ASE
Each visit

Table 5Safety and Efficacy Visits

Monitoring and	Monitoring by dose counts and review of diary entries
Counseling	

4.3.1 Pharmacokinetic study

Specific goals of the study pharmacokinetic analysis will include 1) confirming estimates of PK parameters obtained during phase I, in which only a small number of chronic hepatitis C patients were enrolled, 2) a comparison with the NASH population, 3) identifying the sources and magnitude of intersubject pharmacokinetic variability on the basis of covariates, 4) observing changes in metabolite kinetics over time, and 5) potentially linking safety and outcome measures to pharmacokinetic profiles. The specific analyses are outlined below in section 6.4.

Subjects

The PK sub-study will provide samples according to the limited sampling strategy described below and will be used to develop a more robust population PK model and will also provide for an evaluation of the extent of intra-subject variability influencing covariates under investigation. All patients enrolled in the main study will be eligible to participate in the PK sub-study until the PK sub-study groups are filled. Of the 51 subjects in each dose group (3 dose groups = 153 total subjects), 10 subjects will initially be consented to participate in the PK sub-study and will have additional blood and urine samples collected according to the following design.

Replacement dropouts

The PK sub-study is using this limited subset of subjects to "predict" PK of the study population as a whole. For this reason participants who drop out the PK study will be replaced to successfully fill each dose group.

Sampling Design

A limited sampling strategy will be employed in which a total of 27-30 ml (9-10 samples x 3 ml/sample) of blood will be drawn per patient for quantifying silymarin isomers. Sampling time windows have been selected to optimize PK information from a sparse sampling schedule based on our preliminary model. The 10 subjects in each dose group will be randomly assigned by the Data Coordinating Center to either Schedule 1 or 2 which will require additional PK sampling at 3 or 4 of the clinic study visits; 5 of these subjects will be sampled on Weeks 0, 12, and 24, while the other 5 subjects will be sampled on Weeks 2, 8, 20. Actual sample collection times will be recorded on the case report forms and be utilized in the subsequent analyses.

Sequential blood samples will be obtained from each subject on the same day according to the sampling schedule into which the subject is assigned.

Schedule 1: First Dose: Week 12: Week 24, Last dose: Week 24, 18-24 hrs following last dose: 0-1 hours, 1-3 hours, 3-6 hours 0 hour (trough), 1-2 hours, 2-4 hours 0 hour (trough), 4-6 hours 1 to 2 samples between 18-24 hours following last draw above*

^{*} Time of visit relative to administration of last dose. If close to 18 hrs at time of visit then also collect a 22-24 hrs time point depending on length of stay. If 22-24 hrs at time of visit then only

Schedule 2:	Week 2:	0 hour (trough), 1-2 hours, 2-4 hours
	Week 8:	0 hour (trough), 1-2 hours, 2-4 hours
	Week 20:	0 hour (trough), 1-2 hours, 2-4 hours

Additional Random PK Samples from Subjects Not Participating in the PK Sub-Study

At the time of a scheduled study visit at baseline and treatment weeks 2, 4, 8, 12, 20 and 24, which can be any time during the day, 3 ml blood samples will be obtained from all other study subjects not participating in the PK sub-study. Study coordinators will record the time of the most recent dose from subject report and record the time of sample collection. The inclusion of this sampling scheme will be used to further develop a robust population PK model and will provide for an evaluation of the extent of inter-subject variability influencing the covariates under investigation. Plasma will be obtained for determination of silymarin (Legalon[®]) and silymarin metabolite concentrations (silibinin A and B, isosilibinin A and B, silicristin, and silidianin). Special attention will be paid to recording in source documents accurate sample collection times and timing of previous silymarin dose. Serum concentrations of free and total silymarin isomers will be quantified using LC/MS. Determination of the total fraction will be accomplished after hydrolysis with glucuronidase/arylsulfatase. The extent of phase 2 metabolism will be calculated as the difference been the total and free fractions for each isomer.

Blood

Blood will be collected from each subject for plasma silymarin concentration determination at the times indicated in the schedule of events tables. Plasma will be obtained from collected blood samples and processed and stored according to study procedures.

Urine

One 10 ml aliquot of urine from each visit will be taken and frozen for determination of silymarin concentrations.

Analysis of silymarin concentrations in plasma and urine will be performed using validated analytical methods. All biological samples will be processed and stored according to study procedures.

The label for each sample will identify the subject number and collection date and time.

4.4 Follow-up period: Participants will be followed for an additional 12 weeks after end of treatment. They will return for post-treatment visits at follow-up weeks 4 and 12. During these visits, participants will be evaluated for resolution of adverse events and laboratory studies will be drawn to measure efficacy.

Table 6 Follow-up Visit Procedures

Interim Medical History	
Symptom-directed Physical Exam	Vital signs, weight, and physical exam as needed

1 draw is needed. Prefer two draws in this window in order to determine the terminal half-life of the drug. The draws need to be at least 2 hrs apart.

Adverse Event Assessment	Each visit	
Concurrent		
Medication	Each visit	
Assessment		
CBC/Differential	Each visit	
Chemistry	Each visit: ALT, AST, AlkPO4, total bilirubin, albumin, uric acid, BUN,	
	creatinine, glucose	
Pregnancy Test	Urine, Post-treatment week 4 only	
Sample Storage	5ml serum and 3ml plasma at week 4 only	
HCV RNA	Week 4	
Questionnaires	Week 4: SF-36, CLDQ, CES-D ASE	

4.5 Unscheduled visits: Participants who have changes in severity or initiation of new symptoms, or who need to have laboratory tests repeated, will be asked to return to the study site for unscheduled evaluations.

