The Phase I protocol indicated that decisions regarding dose selection for the Phase II trial would be primarily based upon consideration of safety and the PK relationships observed for the sum of parent (i.e. "Free") silymarin flavonolignan concentrations (i.e. Σ Free silymarin). However, an unexpected finding from the Phase I study was that Σ Free silymarin accounted for only 1.1% to 2.6% of the Total concentrations of silymarin flavonolignans found in the blood for all HCV dose groups (Appendix 1, Table 3). The remaining flavonolignan species that contribute to Total concentrations consist of glucuronide and sulfate conjugates (i.e. metabolites) of the parent flavonolignans.

Therefore, use of Σ Free silymarin concentrations to assess drug exposures will be imprecise since they do not represent the total amount of drug entering the body. In addition, since conjugate concentrations in blood are approximately 11.5-times greater than "Free" concentrations, a small reduction in the extent of silymarin's metabolism to conjugates would be expected to greatly influence "Free" blood concentrations without changing "Total" blood concentrations or Σ Total silymarin exposures. In addition, small changes in the extent of conjugation are not easily detected in "Total" concentrations because of the high %CV in these measures. Nonetheless, "Free" parent concentrations are expected to have influences on the efficacy and safety of silymarin that must be considered independent from those associated with "Total" silymarin flavonolignan concentrations (i.e. unconjugated or "Free" flavonolignan plus all flavonolignan conjugates).

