Parent ("Free") silymarin flavonolignans undergo extensive first-pass phase 2 metabolism to glucuronide and sulfate conjugates in the GI tract and in the liver. Therefore, "Total" flavonolignan concentration, which represents all species of a flavonolignan in blood, is the best measure of the amount of a flavonolignan entering the body following an oral dose. Because any or all of the silymarin flavonolignans may contribute partially or fully to the pharmacological activity of silymarin, Σ silymarin concentration, which represents the sum of the concentrations of all six major silymarin flavonolignans, is the best measure of silymarin exposure for assessing safety and efficacy endpoints. Given these considerations, mean Σ Total silymarin AUC was chosen for assessing dose-exposure proportionality in the Phase 1 trial and provides the basis for selecting 420 mg and 700 mg doses administered three times daily in this Phase 2 study.

Rationale for Dose Selection

High Dose: 700 mg silymarin three times daily

Dose-proportional increases in Σ Total silymarin exposures were observed across all HCV dose groups (Appendix 1, Table 5). Therefore, Σ Total silymarin exposures are predictable and reliable up to 700 mg in HCV patients. Also, a dose of 2100 mg daily (700 mg administered thrice daily) appeared to be safe and well tolerated in patients with HCV (Appendix 2). The 5 adverse events in 4 of 30 patients randomized to Legalon[®] were mild to moderate in severity and 4 of them were thought to be unrelated to treatment. Dizziness, the one adverse event considered to be possibly related to Legalon[®] was self-limiting and resolved in less than 1 day. There were no adverse events reported with doses above 840 mg/day. Since AEs were not observed at the highest exposures obtained with a dose of 700 mg, the silymarin dose of 700 mg administered three times daily that will be used as the high dose for this SyNCH Phase II trials is expected to provide reliable exposures and to be safe and well tolerated in the HCV population. In addition, this dose burden (5 pills three times daily) is the largest at which good patient compliance can be expected.

Low Dose: 420 mg silymarin three times daily

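### Total minus Free is the conjugate concentration, not the extent of phase 2 metabolism; at the protocol's own figures it nearly equals Total

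*Protocol*

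**What the plan says.** Section 4.3.1 describes the assays for the random samples in three steps.

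- What is measured: "Serum concentrations of free and total silymarin isomers will be quantified using LC/MS".
- Total is the result obtained once the conjugates have been split by enzymes.
- The derived measure is then defined: "The extent of phase 2 metabolism will be calculated as the difference been the total and free fractions for each isomer".

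The dose-selection text in section 1.0 supplies the figures needed to judge that measure.

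- In Phase I, summed Free silymarin "accounted for only 1.1% to 2.6% of the Total concentrations of silymarin flavonolignans found in the blood", across all HCV dose groups.
- In the next paragraph, "conjugate concentrations in blood are approximately 11.5-times greater than" Free concentrations.
- A modest fall in conjugation is expected to raise Free a great deal and leave Total unchanged. Further, "small changes in the extent of conjugation are not easily detected in" Total concentrations, because those have a high %CV (no value is given).
- Summed Total exposure was dose-proportional, and 420 mg is expected to give 40% lower exposure than 700 mg.

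Section 4.3.1 lists following metabolite kinetics over time, and possibly linking safety and outcome to pharmacokinetic profiles, among the goals. Section 6.4 plans a population model, covariate effects and logistic regression on metrics such as AUC. It names no ratio of conjugate to parent.

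**The concern.** The extent of a metabolic step is a relative quantity: what share of the drug present has been converted. The stated formula is an absolute one, because the *fractions* it subtracts are concentrations measured with and without hydrolysis. When Free is a very small part of Total, subtracting it hardly changes anything, so the measure called extent behaves like Total.

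Two consequences follow. The measure moves with dose, adherence and time since dose even if conjugation is constant. It also stays nearly still when conjugation changes, which is the one thing its name promises to show. The dose-selection text already describes this weakness for Total, and section 4.3.1 then adopts a quantity almost identical to it. At stake is the interpretation of a secondary pharmacokinetic result: a report of extent built on this formula could not separate altered conjugation from altered exposure.

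**Working it through.** **Inputs.** Free share f = Free/Total = 0.011 to 0.026 (section 1.0, isomer sum). Stated conjugate-to-Free ratio 11.5 (same section). Dose-proportional summed Total, doses 420 and 700 mg (section 1.0).

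**1. The protocol's own figures.**
- Lower exposure at 420 mg: 1 − 420/700 = 0.40. The stated 40% reproduces.
- Conjugate/Free = (1 − f)/f. At f = 0.026: 0.974/0.026 = 37.5. At f = 0.011: 0.989/0.011 = 89.9. The stated 11.5 does not reproduce.
- In reverse, 11.5 gives f = 1/(1 + 11.5) = 8.0%. Reading 11.5 times greater as 12.5-fold gives 1/13.5 = 7.4%. Reading it as Total/Free gives 1/11.5 = 8.7%. No reading reaches 1.1% to 2.6%.

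**2. How close is the difference to Total?** (Total − Free)/Total = 1 − f.

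| f | (Total − Free)/Total |
|---|---|
| 1.1% | 98.9% |
| 2.6% | 97.4% |
| 8.0% (from 11.5-fold) | 92.0% |

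**3. Dependence on dose at equal conjugation.** 700(1 − f) / [420(1 − f)] = 1.67 for any f. If conjugation were actually lower at the high dose (f = 1.1% at 420 mg, 2.6% at 700 mg), the measure would still rise: 700 × 0.974 / (420 × 0.989) = 1.64.

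**4. Reaction to a change in conjugation, Total fixed.**
- f from 1.1% to 2.6%: 0.974/0.989 − 1 = −1.5%.
- f doubled: −1.1% from 1.1%, −2.7% from 2.6%, −8.7% from 8.0%.

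**5. The same change on a ratio scale.** f from 1.1% to 2.6% multiplies Free/Total by 2.6/1.1 = 2.36 and conjugate/Free by 37.5/89.9 = 0.42. A change of dose at fixed f leaves both ratios where they were.

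**6. The other reading of *fraction*.** If it meant a proportion of Total, the difference would be 1 − f. The dependence on dose would vanish, but the measure would still move only from 0.989 to 0.974, the same 1.5%. The assay wording does not support this reading in any case.

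**The case against.** The sentence closes an assay description and feeds no named analysis. Total minus Free is a correctly derived conjugate concentration, and since the metabolites are conjugates, it is a proper input for metabolite kinetics. Free and Total are both measured for each isomer, so any ratio can be computed later. On this view only a loose label is wrong.

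Much of this stands, and it rules out several stronger readings that a reader might infer.

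- *A doubling of Free would go unseen.* It would not: Free is assayed in its own right, and section 1.0 says its influence must be considered separately from that of Total.
- *The trial will report more metabolism at 700 mg.* Section 6.4 plans no comparison of Total minus Free between doses, so this is a risk of the definition and not a planned result.
- *The protocol concedes that changes in conjugation cannot be seen in Total.* It says only that small ones are hard to detect, and it gives no CV. A power statement would rest on assumed values.
- *The 11.5 figure undermines the doses.* The doses rest on mean summed Total AUC, and no calculation shown uses 11.5.

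Two further limits stand. The 1.1% to 2.6% is a range for the isomer sum across Phase I dose groups, not a within-patient change, and isomer-level shares are not in the text. And a ratio is not automatically clean: random samples are drawn at whatever hour the visit falls, and a single-sample ratio can vary with time since dose unless parent and conjugates run in parallel, which the documents do not establish.

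The objection does not rescue the label. The protocol states a formula for extent, and nothing in section 6.4 replaces it with a normalised measure.

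**Conclusion.** The point holds as a fault in the stated measure. What section 4.3.1 calls extent is the conjugate concentration: about 97% to 99% of Total at the reported free share, and 92% even at the 11.5-fold figure. The conclusion is therefore the same whichever Background figure is right. The 1.5% and 1.67-fold results assume that figures for the isomer sum roughly apply to single isomers, and that dose-proportionality of summed Total AUC carries over to single-isomer concentrations. An isomer with a larger free share would react more.

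The consequence is limited to the secondary pharmacokinetic objective; the ALT and safety analyses are untouched. It should be corrected because the measure does not show what it is named for and the remedy is nearly free. The mismatch between 11.5 times and 37 to 90 times is a separate, minor contradiction in background text.

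**What to change.** In section 4.3.1, keep Total minus Free under the name of conjugate concentration. Define the extent of phase 2 metabolism, per isomer and for the sum, as Free/Total or conjugate/Free, analysed on the log scale. Preferably derive it from the AUC or model-based estimates already planned in section 6.4. If single samples are used, account for time since dose. State how Free values below the assay limit are handled as censored.

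In section 1.0, check the 11.5 figure against the Phase I tables and either correct it or say which quantity it describes, so that it agrees with the free share of 1.1% to 2.6%.

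The cost is a few sentences in section 4.3.1 and one background figure. Samples, assays and visits are unchanged. The only added analysis work is the treatment of time since dose and of low Free values.
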